15. STATISTICAL CONSIDERATIONS

Randomisation

 Table 6: Randomisation Summary

Randomised design	Individual patient		
Type of randomisation	Randomly permuted varying length blocks, stratified by:		
to be used			
Stratification variables	- Site		
	- Young person currently taking a therapeutic does of antidepressant: Yes/No		
	- Young person's total RCADS score above a T score of 70 versus a score 70 or		
	below		
Ratio allocation	1:1 ratio		
between treatment			
arms			
How randomisation will	A web-based randomisation system designed and maintained by the King's		
be implemented and	College London Clinical Trials Unit (KCTU) for the duration of the project. Access		
approach to conceal	will be restricted via usernames and passwords to appropriate research team		
allocation	members, and the system will be hosted on a dedicated server within KCL.		
Define the	As this is not a drug trial, and it is not possible to blind the participants and		
circumstances under	certain trial team members to allocation, we will not need a special procedure		
which randomisation	for code breaking. We do not anticipate serious adverse reactions, but if there		
codes may be broken	is a serious adverse event and there is a need for a blinded member of the trial		
and the procedure for	team to know if an individual is in the MAC group, the individual, their carer, or		
doing it	one of the trial therapists can provide this information.		

Following written consent, participants will be randomised in a 1:1 ratio to one of the two treatment arms (TAU, or MAC + TAU). A web-based randomisation system will be designed, using the bespoke KCTU randomisation system. The randomisation system will be created in collaboration with the trial analyst/s and the CI and maintained by the King's Clinical Trials Unit for the duration of the project. It will be hosted on a dedicated server within KCL. The system will employ block randomisation with randomly varying block sizes and will be stratified by i) site, ii) if the young person is taking a therapeutic dose of antidepressants or not and iii) if their RCADS (Ebesutani et al., 2012) score at baseline indicates that they have severe depression or not. The details needed for randomisation will be held in a dedicated database. Only the Programme Manager, Trial Manager and Programme Administrators (unblinded) will have access to the randomisation system (or their nominated backup in times of absence; the nominated backup will not be another member of the blinded team but will be a team member whose role on the delegation log specifies this role as contingency Trial Manager).

Sample size calculation

Our power calculation suggests that 480 participants (240 per arm, MAC allocation=20 groups) will allow us to detect an effect size of 0.3 with 90% power, allowing for 20% attrition. The calculation assumed using a two-sided independent samples t-test of the difference between arms, alpha = 0.05, assuming a MAC group size of 12, intraclass cluster correlation of 0.05, i.e. a design effect / inflation of $1 + [12 - 1] \times 0.05 = 1.55$ (Williams et al., 2008), one baseline and two post-randomisation measures with correlation rho = 0.5 = deflation factor of 0.5 (Machin et al., 2009), and 20% attrition (Kennard et al., 2009;(Mental Health Taskforce, 2016). The calculation was done using the Gpower software, with methods from Killip et al used to hand-calculate the cluster effect for MAC group (Killip, 2004).

We selected this effect size in part because the mean effect size for depression was 0.29 across multiple measures and interventions in a meta-analysis of psychological interventions in children and young people over the last five decades (Weisz et al., 2017). We also note the MFQ (COSTELLO & ANGOLD, 1988) specifically was sensitive to improvement in previous UK-based RCTs of interventions for depression in young people (Goodyer et al., 2008, 2017). Goodier's studies (NG134 2019 Evidence Review A, 2019a;Goodyer et al., 2017) suggest a five-point between group reduction on the MFQ represents the minimally clinically important difference for the assessment of superiority. The ADAPT study found a MFQ standard deviation of 14.6, equating this to an effect size of 0.34 (Goodyer et al., 2008). This suggests our power estimate is conservative, as does the fact that two MAC groups we ran in London after the PDG completed found larger MFQ correlations over time of rho~0.8, whereas we chose to use the more conservative rho = 0.5. To build in a buffer and be conservative, we based our sample size calculation on an effect size of 0.3. While 0.3 represents a small effect size, given the impact of prolonged depression during adolescence and the potential impact of escape from future episodes, combined with the number of young people who could benefit and spillover effects among carers, even this small effect would bring large potential patient and societal benefits. The calculation was simplified with respect to AUC to minimise the complex data structure assumptions made, however, we expect the AUC model with fortnightly measures to increase efficiency, so the sample size is likely also conservative from this point of view.

Blinding

• The senior statistician and senior health economist will not have access to the randomisation list or REDCap database at any point in the trial to remain fully blinded until review of the first draft of the statistical/health economic reports for checking, when they will become fully unblinded.

- Similarly, **the Chief Investigator and Principal Investigators** in each trial centre will remain fully blinded until they review the finalised statistical report, when they will become fully unblinded.
- **The Junior Statistician and Junior Health Economist** will be fully blinded until sign-off of the statistical and health economic analysis plans, after which they will be fully unblinded so they can inspect and utilise app usage/intervention-related data.
- The Programme Manager, Trial Manager and the Trial Administrators will be unblinded.

The only individuals that will be able to summarise/see data by arm prior to the review of the statistical report are the Junior Statistician, Junior Health Economist, and the members of the Data Monitoring Committee. We presume that the Data Monitoring Committee will remain partially blinded and will prepare the closed report accordingly.

No serious harms associated with taking part in the intervention are expected, therefore a formal procedure for unblinding any blinded staff during the study is not needed.

Roles	Individual- level	Method of blinding OR justification for unblinding	Group- level	Method of blinding OR justification for unblinding
Programme Manager	U	Assigns participants to randomisation groups (is not recruiting or assessing participants)	В	No access to randomisation list or data summarised at group-level
Trial Manager	U	Assigns participants to randomisation groups (is not recruiting or assessing participants)	В	No access to randomisation list or data summarised at group-level
Trial Administrator	U	Assigns participants to randomisation groups (is not recruiting or assessing participants)	В	No access to randomisation list or data summarised at group-level
Study Participants	U	Only unblinded to their own allocation (we are unable to blind participants due to the nature of the intervention)	В	No access to randomisation list or data summarised at group-level
Referring Clinician	U	No access to data at the individual level		
Trial Therapists	U/P	Only unblinded to those seen for therapy (required for providing MAC). Information	В	No access to randomisation list or data summarised at group-level

Table 7: Blinding Summary

Roles	Individual- level	Method of blinding OR justification for unblinding	Group- level	Method of blinding OR justification for unblinding
		about other therapists' participants may be mentioned in therapy supervision but is minimised.		
Therapist Supervisor	U/P	Usually blinded (not told of group assignments), unless participant details need to be conveyed for safety or wellbeing purposes	В	No access to randomisation list or data summarised at group-level
Data Collectors / Outcome Assessors	В	Not told of group assignment, participants asked to conceal this, but blinding assessed *	В	No access to randomisation list or data summarized at group-level
Trial Statistician	В	No interaction with individual participants	U	Access to full randomisation list required for data monitoring & analysis. NB only unblinded after an initial draft of the SAP has been signed
Senior Statistician	В	No interaction with individual participants	В	No access to full randomisation list *
Chief Investigators	В	Usually blinded, unless participant details need to be conveyed for safety or wellbeing purposes	В	No access to randomisation list or data summarised at group-level
Independent Members of DMEC	В	No interaction with individual participants	U/P	The level of DMEC blinding will be at their discretion but will likely see data split by group at least a partially blinded level.
TSC	В	No interaction with individual participants	В	No access to randomisation list or data summarised at group-level

U = unblinded, B = blinded, P = partially blinded (i.e., see data split by groups labelled as A/B).

* After data has all been collected, the database locked, the data have been analysed and a first draft of the statistical report has been prepared, the senior statistician will become unblinded to carry out final checks on the analysis code and statistical report.

16. STATISTICAL ANALYSIS

General

Statistical methods are described briefly here. A comprehensive Statistical Analysis Plan (SAP) will be developed and agreed with the Trial Steering Committee (TSC) before any analysis is carried out. The SAP will describe statistical procedures in detail. Please see Section 14 for a description of the measures.

The main analysis will follow the intention to treat (ITT) principle as much as possible (Sullivan et al., 2018; White et al., 2012). We will outline this as our main estimand with further detail in the Statistical Analysis Plan. The analysis will be carried out by the Junior Statistician under the guidance of the Senior Statistician. Analysis will progress once all data have been cleaned and the database locked.

Baseline variables will be summarised by arm and overall, using mean and standard deviation or median and 25th and 75th percentiles for normally distributed/non-normally distributed continuous variables or ordinal variables, and frequencies and percentages for categorical variables. There will be no statistical testing of, or presentation of p-values relating to, differences between the arms.

Primary outcome

The difference between the arms on the primary SMFQ outcome will be estimated using a linear mixed effects analysis of covariance (adjusting for baseline) model, with the fortnightly SMFQ measures as dependent variables, accounting for repeated measures and therapy group clustering and including intervention arm and the stratification variables as independent variables. We intend to estimate the difference in AUC by including an intervention arm by fortnight interaction term, allowing the extraction of weekly/follow-up visit intervention arm difference estimates, and then the calculation of the appropriate linear combination of these estimates (i.e. using the trapezium rule). We may also explore time as a continuous variable in models.

Secondary complier average causal effect (CACE) analyses of the SMFQ primary outcome using instrumental variable/structural equation modelling methods will estimate the treatment effect in those that attend at least 4 MAC sessions (Dubicka & Bullock, 2017) and of those that complete 50% or more of the mindfulness practice (C. Crane et al., 2014), possibly with an exploration of methodology for extending the CACE analysis to the AUC models.

Secondary outcome

The fortnightly PHQ-8 secondary carer outcome will be analysed in the same way as described for the primary outcome. The differences in the other secondary outcomes between intervention arms at 14 weeks and 12-months post-randomisation will be estimated using similar models to that for the primary and PHQ-8 secondary outcome, with 14 week- and 12-months measures of the outcome as dependent variables, and an appropriate link function depending on the form of the variable. Rather than calculating the AUC for these variables, we will include an intervention arm by time point interaction term and extract the differences for each at 14 weeks, and 12 months.

Sub-group (baseline moderator) analysis

Baseline moderators (young people: RCADS score, YCAS score, race/ethnicity, gender, age, on a therapeutic dose of medication for the treatment of depression or anxiety or not, preference for face-to-face or remote) will be analysed by replacing the intervention arm by fortnight interaction term with a baseline variable by intervention arm by fortnight interaction term in the main analysis model described for the primary MAC outcome. If this interaction term suggests there are different effects by different levels of the moderators,

the AUC will be re-estimated for appropriate levels of the moderator. We note that subgroup analyses are not powered for, and so will be exploratory.

Missing Data

Missing data due to loss to follow-up or withdrawal will be accounted for under a missing at random assumption in the mixed effects models estimated using maximum likelihood. To make the missing at random assumption more plausible, we will assess whether baseline variables predict missing data, and included these in the analysis models if so. We may consider multiple imputation if post-randomisation variables predict missing data, and/or missing not at random sensitivity analyses; if so, these will be outlined in more detail in the SAP.

17. MEDIATION ANALYSIS

Decentring

To investigate the purported core mechanisms of the treatment, we will test whether treatment-related changes on the Decentring and Nonreactivity scale of the CHIME/CHIME-A questionnaire mediate change in depressive symptoms in both young people and carers.

Mindfulness skills

To investigate the role of general mindfulness skills, we will investigate whether treatment-related increases in mindfulness skills across all facets of the CHIME/CHIME-A mediate levels of depressive symptoms (i.e., total CHIME/CHIME-A scores across all subscales). To explore the relative contributions of treatment-related changes in mindfulness facets (all the CHIME/CHIME-A subscales) to the mediation of the primary treatment outcome, we will run multiple parallel mediator models using a stepwise approach to enter the different subscales to identify the most relevant facets in both groups, as shown in **Figure 6**.

Figure 6: Graphical representation of mediator models used to investigate the role of general mindfulness skills

Self-compassion

While not explicitly listed in our logic model, we will also investigate potential mediating effects of selfcompassion, a characteristic that is integral to the attitudinal components of mindfulness and has previously been shown to increase following MBIs.

Sequential mediation pathways

Including cognitive targets of decentring and mindfulness skills: To better understand how increases in decentring and general mindfulness skills may impact on symptoms, we will explore pathways in a more comprehensive model that includes cognitive target variables, separately in young people and in adults. Based on previous research, this model assumes that decentring is particularly suited for reducing ruminative tendencies (Wu et al., 2022; Ishikawa et al., 2018), while general mindfulness skills not only support the ability to decentre but benefit emotion regulation more widely (Desrosiers et al., 2014). That is, we assume two separate sequential pathways, one in which decentring reduces rumination thereby reducing symptoms and another in which mindfulness increases emotion regulation skills thereby reducing symptoms, as shown in **Figure 7**.

Figure 7: Graphical representation of sequential mediation models used to investigate the role of decentring and general mindfulness skills

Transfer across the young person-carer dyad

A unique characteristic of our mindfulness-based approach is the use of parallel interventions for young people and their carers to address the interrelated nature of mental health within the family. Parental psychopathology and emotion dysregulation represent an important risk for the development of depression in children and young people (Zhang et al., 2020) and there is increasing evidence that carers shape emotion regulation processes in children across development through several different mechanisms (Silvers, 2022; Martin & Ochsner, 2016).

Decentring and mindfulness

To test such transfer and investigate the degree to which improvements in regulation in carers influence outcome in young people, we will run analyses to investigate mediation of treatment outcome in young people through changes in carer's ability to decentre, more specifically, and mindfulness skills, more generally. As shown in **Figure 8**, we hypothesise that treatment-related increases in carer's ability to decentre and general mindfulness skills will both have a significant mediating influence on young people's symptoms during follow-up.

Figure 8: Graphical representation of mediator models used to investigate the role of changes in carers decentring and general mindfulness and the impact this may have on young people's symptoms

Sequential mediation pathways including mindfulness and relationship quality

Transfer may occur through several mechanisms, including modelling of emotion regulation skills or indirect influences on parenting behaviours and the wider emotional context within the family, which we assume to become reflected in changes in perceived adolescent-carer relationship quality. To explore these mechanisms in more detail, we will test pathways within a comprehensive model considering potential influences of mindfulness skills on perceived relationship quality, as shown in **Figure 9**. Relationship quality will be assessed from both the young person's and the parent's perspective using the Parent-Adolescent Relationship Scale (Burke et al., 2021), administered to all individuals in the trial.

Figure 9: Graphical representation of sequential mediation models used to investigate the role of family relations, mindfulness skills and young person's symptoms

Mediation of the effect of practice in the intervention arm only

We will test, in young people and in parent/carers, whether the degree to which they engage in practice during the intervention is related to changes in decentring and mindfulness skills over the period of the intervention, and to levels of symptoms measured using the SMFQ. We assume that regular practice is necessary for effective development of the treatment-related skills that serve to reduce depression and will test the hypothesis that effects of practice on depressive symptoms during follow-up are mediated through changes in decentring and general mindfulness skills during the intervention, both in young people and in adults who participated in MAC. We will use similar methods to those described above for the other mediation modelling, but will just model data from the individuals in the MAC arm, i.e., those for whom we can measure engagement in practice.

Mediation analysis methods

Mediation will be evaluated using structural equation modelling and/or causal mediation analysis methods adjusting for the stratification variables and baseline measures where appropriate (i.e., adjusting for baseline measures of mediator and outcome in mediator models (Dunn et al., 2015) and using appropriate modelling methods (i.e., temporally ordered mediator and outcome, longitudinal models where appropriate). Given previous research on MBCT that has provided evidence for the importance of acquisition of therapy-related skills across the intervention period (C. Crane et al., 2014), as well as their refinement and continued utilisation after the end of the intervention (Segal et al., 2019), we will run separate sets of analyses to test mediation of outcome at the end of intervention and at the end of follow-up. We may explore the extension of this methodology to repeated measures/AUC models. If we find significant baseline moderators of treatment effect, we may explore whether there is mediated moderation (Dunn et al., 2015; Muller et al., 2005). All mediation models will use raw mediator and outcome scores adjusted for baseline scores, rather than change scores (Landau et al., 2018).

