Following consultation with our Patient and Public Intervention (PPI) group, we will ask a bespoke question about participants' perception of their ability to cope with life on a 5-point Likert scale.

Parent-Adolescent Relationship Scale PARS; (Burke et al., 2021).

Critical Dimensions of the parent–adolescent relationship will be assessed from multiple perspective using the Parent Adolescent Relationship Scale (Burke et al., 2021). The PARS is a 20-item measure that comprises three subscales: connectedness, shared activities, and hostility. Initial research has demonstrated good discriminant and convergent validity (Burke et al., 2021).

Mediators

Collected at T0, T1, T2:

PARS (Burke et al., 2021) (above) is also a mediator.

CHIME-S (Karl et al., 2024)/CHIME A (C. Johnson et al., 2017)

The Comprehensive Inventory of Mindfulness Experiences CHIME; (Karl et al., 2024) is an established selfreport questionnaires available in parallel versions for adults (Bergomi et al., 2014; S. Wilkinson et al., 2023) and adolescents (C. Johnson et al., 2017). The CHIME-S and CHIME-A cover mindfulness as a complex construct consisting of the following facets (subscales):

• Awareness of Internal Experience,

- Awareness of External Experience,
- Acting with Awareness,
- Accepting and Nonjudgmental Orientation,
- Decentring and Nonreactivity,
- Openness to Experience,
- Relativity of Thoughts, and
- Insightful Understanding.

They will be administered at all main trial assessment points for all individuals, young people, and carers.

Self-Compassion Scale Short Form SCS-SF; (Raes et al., 2011)

The SCS-SF (Neff, 2016; Raes et al., 2011) is a 12 item self-report measure of self-compassionate responding in the event of failure and distress. Items are rated on a five-point scale from 1 (almost never) to 5 (almost always). The measure has excellent internal consistency (α = .89) as well as good convergent, divergent, content and face validity (Raes et al., 2011).

Emotion Regulation Questionnaire ERQ; (Gross & John, 2003)

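### The general-mindfulness mediator is the full CHIME total, which contains the decentring mediator, so its indirect effect does not represent a route separate from decentring

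*Protocol*

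**What the plan says.** Section 17 names two mediators from the same questionnaire.

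- **Decentring.** The test is whether "treatment-related changes on the Decentring and Nonreactivity scale of the CHIME/CHIME-A questionnaire mediate change in depressive symptoms". The mediator is one subscale.
- **General mindfulness.** The test is whether these skills "mediate levels of depressive symptoms (i.e., total CHIME/CHIME-A scores across all subscales". The mediator is the total, with no subscale left out.

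Section 14 (Mediators) lists eight facets for the CHIME-S and CHIME-A, and "Decentring and Nonreactivity" is one of them.

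Section 17 then uses the pair in three further places:

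- **Sequential model:** "we assume two separate sequential pathways, one in which decentring reduces rumination thereby reducing symptoms". The other pathway runs from mindfulness through emotion regulation. The stated rationale is that "general mindfulness skills not only support the ability to decentre but benefit emotion regulation more widely".
- **Carer-to-child transfer:** "increases in carer's ability to decentre and general mindfulness skills will both have a significant mediating influence".
- **Practice analysis (MAC arm only):** effects of practice are to be mediated through both decentring and general mindfulness.

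For the facets themselves the plan is different: "we will run multiple parallel mediator models using a stepwise approach to enter the different subscales". Those models use subscales that share no items.

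**The concern.** By these definitions the first mediator is a component of the second. Two consequences follow.

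1. If MAC changes decentring and nothing else, the total rises too. An indirect effect through the total can then be found although none of the other seven facets moved.
2. The assumption that mindfulness supports decentring would be assessed partly by letting a score predict its own part.

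Objectives 5 and 6 in Section 9 ask by which pathways MAC works, within the young person and across the dyad. Section 17 treats decentring as the core mechanism. If a pure decentring effect can register as a general-mindfulness route, the answer to that question is compromised. The primary SMFQ comparison is not involved.

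**Working it through.** The protocol states no figure on this point, so there is nothing to reproduce. The check has three steps.

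**Inputs.** From the protocol: 8 facets (Section 14); the total taken over all of them (Section 17); 480 randomised with 20% attrition (Section 15), giving 480 × 0.8 = 384 analysed. Assumed, because the protocol does not give them: facets of equal variance and equal weight with a common correlation r, shown from 0 to 0.6.

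**Step 1: overlap built in by the scoring.** Write D for decentring, R for the sum of the other seven facets, and T = D + R.

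- corr(D, T) = (1 + 7r)/√(8 + 56r) = √((1 + 7r)/8)
- corr(D, R) = 7r/√(7 + 42r)
- variance inflation factor (VIF) with D and T in one model = 1/(1 − corr(D, T)²)
- shift in T, in SD units, from a 0.5 SD arm effect on D alone = 0.5/√(8 + 56r)

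| r | corr(D, T) | corr(D, R) | Difference | VIF | Shift in T |
|---|---|---|---|---|---|
| 0 | 0.35 | 0.00 | 0.35 | 1.14 | 0.18 SD |
| 0.3 | 0.62 | 0.47 | 0.15 | 1.63 | 0.10 SD |
| 0.5 | 0.75 | 0.66 | 0.09 | 2.29 | 0.08 SD |
| 0.6 | 0.81 | 0.74 | 0.07 | 2.86 | 0.08 SD |

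**Step 2: total as the only mediator.** In simulated trials (N = 384, 3,000 runs per setting, joint-significance test), the arm changes D only and the outcome depends on D only, so the other seven facets mediate nothing. The table shows how often general mindfulness is declared a mediator when scored as T.

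| r | arm effect 0.3 SD | 0.5 SD | 0.8 SD |
|---|---|---|---|
| 0.1 | 11% | 24% | 53% |
| 0.3 | 9% | 17% | 35% |

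Across all settings, including r = 0.5, the range is about 9% to 53%. With R in place of T it is 2% to 5%.

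**Step 3: decentring and total in one model.** Suppose the outcome is b_D·D + b_R·R. Substituting R = T − D gives (b_D − b_R)·D + b_R·T. The coefficient on T is therefore the effect of the other seven facets. The coefficient on D is its own effect minus theirs. Both are estimable. The difficulty lies in the arm-to-mediator path. If the arm raises D by a and leaves R unchanged, it also raises T by a. The model then credits:

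- a·b_R to general mindfulness
- a·(b_D − b_R) to decentring

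The sum, a·b_D, is right but the split is not. With R as the second mediator, its arm path is 0 and the full a·b_D goes to decentring.

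Whether this shows depends on b_R. With b_R = 0, the simulations flag T falsely in 3% of runs or fewer. When the other facets do predict symptoms, and the arm still moves decentring only (N = 384, r from 0 to 0.5), the joint model flags T as a mediator in 7% to 80% of runs, against about 4% to 6% with R.

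**The case against.** The case on the other side is substantial.

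- **The scores can be separated.** A reader might infer from the overlap that the two mediators share all their items, or are too collinear to tell apart. The documents do not support that. Only one facet of eight is shared, the VIF is 1.1 to 2.9 over the assumed range, and a joint model fits exactly as well with the total as with the seven-facet score. This part of the objection stands. It does not rescue the indirect effect through the total, because the arm-to-total path still carries the decentring change (step 3).
- **The nesting may be intended.** The transfer section presents decentring as the specific skill and mindfulness as the general one, and does not call them distinct. A decentring-driven rise in the total is then a legitimate broad-construct effect. This is fair for the stand-alone model. It does not fit the sequential model, which calls the pathways separate.
- **The facet models already attribute effects.** They share no items and can show whether decentring drives the total's result. That mitigates the stand-alone analysis, but it does not change the score used in the sequential, transfer or practice models.
- **Model detail is open.** Figures 7 to 9 could not be consulted, the sequential subsection does not restate the scoring, and the choice between structural equation and causal mediation methods is left open. Whether the two mediators enter jointly is therefore not settled. The scoring rule itself is stated in the protocol, and the same terms are reused without redefinition.
- **The overlap may be small.** At r = 0.6 the correlation difference is 0.07. This is correct, and a difference in correlations is not itself a bias in an indirect effect.

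**Conclusion.** The point holds as a flaw in secondary, partly exploratory mechanism analyses. As scored, the general-mindfulness mediator contains the decentring mediator, so its indirect effect cannot be read as a route separate from decentring.

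The overlap adds 0.35 to the correlation at r = 0, falling to 0.07 at r = 0.6. In the simulations a decentring-only effect is labelled general-mindfulness mediation in about 9% to 53% of trials when the total is the only mediator. In the joint model it is 7% to 80% when the other facets also predict symptoms. These rates rest on assumed facet correlations, equal facet variances and assumed arm effects of 0.3 to 0.8 SD in the single-mediator runs. They show that the error can arise and do not forecast its frequency in this trial.

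A reader might go further and conclude that the trial will report a mindfulness route that does not exist. The documents do not support that: it depends on how MAC acts on the facets and on model details that the text leaves open. The effectiveness conclusion and sample size are untouched.

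**What to change.** In Section 17, and in the SAP to match, add one scoring rule. In the sequential, carer-transfer and practice-mediation analyses, wherever decentring and general mindfulness are modelled together or interpreted as distinct routes, score general mindfulness over the other seven CHIME/CHIME-A subscales, excluding Decentring and Nonreactivity.

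The full total may stay in the stand-alone mindfulness model as a broad construct. Add a sentence there saying that a positive result is not evidence of a route distinct from decentring.

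The cost is a line of scoring and a line of interpretation, with no new data. The downside is that the seven-facet score is not the total the protocol now specifies, so the change should be recorded before any mediation analysis is run.
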